- Toxicity (gastrointestinal, hematologic, dermatologic, cardiac,

pulmonary, hepatic, renal, infection, skeletal, etc.)

Other important clinical factors

- Comorbidity
- Concomitant medication

- Prenatal development
- High-risk pregnancy
- Delivery complications including hypoxia
- Gestational time at the delivery
- APGAR score
- Gestational weight (IUGR)
- Psychomotor development impairment and psychiatric conditions recognised prior to the therapy
- Pregnancy and breastfeeding status after blinatumomab initiation
- Study Sample Size

The targeted sample size for this study is approximately 298 patients. However, the actual number of patients that will be included in the study will depend on the results of site feasibility, willingness of patients (or their legal guardians/caregiver) or sites to participate in the study.

• Data Analysis

Continuous variables will be summarized by mean, median, standard deviation, lower and upper quartiles, and minimum and maximum values. Categorical variables will be summarized by number and percentage of patients in each category. For categorical outcomes, 95% confidence intervals (CIs) will also be presented where appropriate. For time-to-event endpoints, Kaplan-Meier (KM) curves and KM proportions at select time points, the numbers of patients with events and then number of patients censored will be used to summarize the data.

A comparison between the blinatumomab versus chemotherapy group will be conducted at the final follow-up in the study pending adequate sample size is enrolled (\geq 50 patients per arm) and the blinatumomab and SOC groups are comparable (eg, there is overlap between PS distributions across the two groups, or no critical differences that cannot be accounted/adjusted for). Prior to comparison being conducted, covariates listed in Section 9.3.2 will be evaluated for differences between the two groups. Any covariates that are not comparable between the two (Wald chi-square or t-test, p-value < 0.25), will be evaluated as a covariate for adjustment in the models. A multivariate logistic regression will be used to compare incidence event objectives and Cox regression will be used to compare time-to-event objectives. Also, we will conduct a propensity score weighting analysis based on the covariates collected for this study.

This study will have 5 interim analyses, taken at 2-year intervals over the course of the 12-year follow-up. A final report will be produced at the end of the study.

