7.3 Statistical Inference

The study will compare blinatumomab therapy versus chemotherapy for the occurrence of neuropsychomotor developmental impairment, neurological impairment, endocrine impairment, and immune system impairment.

8. Research Question and Objectives

The overarching aim of this study is to describe and compare the long-term safety profile of B-precursor ALL paediatric patients who have been treated with either blinatumomab or chemotherapy prior to undergoing alloHSCT.

Primary 8.1

Primary Objective					
Objective	Endpoint				
 To estimate incidence of neuropsychomotor developmental impairment, endocrine impairment, neurological impairment, and immune system impairment (including auto-immune disorders and vaccine failure) 	 Impairment defined as any of the following: Neuropsychomotor development impairment in any area of social and emotional, language/communication, cognitive, or motor Neurologic impairment defined as any peripheral nervous system disorders including neuromuscular junction disorders; central nervous system disorders Endocrine impairment defined as any Hypothalamus-Pituitary-Gonadal Axis disorders; Hypothalamus-Pituitary-Adrenal (HPA) Axis disorders; Hypothalamus-Pituitary-Thyroid Axis disorders Immune system impairment defined as any leukopenia (neutropenia and/or lymphopenia); low IgG; low IgM, and; low IgA; autoimmune disorders; vaccination failure 				

8.2	Secondary
•	

• To estimate the incidence of Haemopoietic Stem Cell Transplant (HSCT) related adverse events (AEs)	 HSCT-related AEs defined as any second malignancy; Graft versus Host Disease (GvHD); infection, and/or; relapse
 To estimate the incidence of subsequent relapse of leukemia including in the central nervous system (CNS) 	 Relapse is defined as any of the following: Isolated bone marrow relapse (M3³ in the absence of extramedullary involvement) Combined bone marrow response (M2 or M3 marrow and at any extramedullary manifestation of ALL) Extramedullary relapse (either CNS relapse, testicular relapse, or relapse at other sites⁴)

³ Cytological bone marrow assessment grading: see Appendix F for details
 ⁴ See Appendix F for relapse criteria (including extramedullary relapse)

 To estimate the cumulative incidence of long-term AEs 	 AEs in any of the following organ systems: gastrointestinal, hematologic, dermatology, cardiac, pulmonary, hepatic, renal, neurological, infection, immunology, and skeletal

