9.2.1 Study Period

Enrolment of patients into 20180130 will occur if they meet all eligibility criteria. All eligible patients or their caregivers/legal guardians will be approached to provide informed consent for participation. Once informed consent has been given, and all inclusion/exclusion criteria are met, the patient will be enrolled via interactive response technology (IRT) in the study and data collection will begin. The study will commence at the first data collection of the first site. Patients will be followed for a maximum of a 12-year period or up to the age of 25 years, death, withdrawal of consent, or loss to follow-up, whichever comes first. The study will end when 12 years of follow-up for the last patient (if the patient has not withdrawn consent, been lost to follow-up, or died before the end of the 12 years of follow-up) is completed. If the last patient enrolled on study dies or is lost to follow-up before the 12 years following alloHSCT, the remainder

of the patients on study will continue to be followed until all patients on study have reached 12 years following alloHSCT, until death, withdrawal of consent, or lost to follow-up, whichever occurs first.

Data will be entered into an eCRF and will encompass information abstracted from patient charts from routine clinical visits. Data abstraction will be performed approximately every 6 months (± 30 days) starting at enrolment. Additional data on neuropsychomotor development will be assessed through specific questionnaires (paper and/or electronic) which will be administered at pre-specified intervals starting at enrolment (approximately every 6 months [± 30 days] for patients up to 6 years old and approximately yearly [± 60 days] for patients from 6 years old).

The first day of follow-up (day 1) will be the date of successful completion of alloHSCT (following chemotherapy/ blinatumomab treatment).

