9.2.5 Study Follow-up

This is a prospective study where data will be collected at routine clinical visits which will occur per standard of care (for a period of up to 12 years). A total of 12 years follow-up or 144 months of follow-up is planned for study 20180130. At each data collection stage, relevant information will be retrieved from patient charts subsequent to the preceding data abstraction time point to ensure there is no gap in data collection. Data abstraction will be performed approximately every 6 months (± 30 days) starting at enrolment. Additional data on neuropsychomotor development will be assessed through specific questionnaires (paper and/or electronic) which will be administered at pre-specified intervals starting from enrolment (approximately every 6 months [± 30 days] for patients up to 6 years old and approximately yearly [± 60 days] for patients from 6 years old). For each enrolled patient, data collection will end at 12-years of follow-up, the age of 25 years, loss-to-follow-up, withdrawal of consent, or death, whichever occurs earliest. All treatments for ALL will be captured in this period.

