9.7.2.2.3 Analysis of the Primary and Secondary Endpoints

Patient incidence proportions (and 95% Cls) for each of the specified outcome events will be summarized. KM estimates for time to first onset of each specified event will be provided.

For the events of interest, events that occur after a relapse or secondary malignancy will be censored as it is unlikely that events that occur after relapsed and treatment for relapse could be considered related to initial chemotherapy or blinatumomab treatment for the prior disease occurrence.

A comparison between the blinatumomab versus chemotherapy group will be conducted at the final follow-up in the study pending adequate sample size is enrolled $(\geq 50 \text{ patients per arm})$ and the blinatumomab and SOC groups are comparable (eg. there is overlap between PS distributions across the two groups, or no critical differences that cannot be accounted/adjusted for). Prior to comparison being conducted, covariates listed in Section 9.3.2 will be evaluated for differences between the two groups. Any covariates that are not comparable between the two (Wald chi-square or t-test, p-value < 0.25), will be evaluated as a covariate for adjustment in the models. The primary and secondary endpoint of discrete events (eg, incidence endpoints) will be compared by a logistic regression which will generate an odds ratio and 95% confidence interval of the odds of developing an event. Endpoints that are time-to-event will be compared by a Cox regression model which will generate hazard ratio and 95% confidence interval for the risk of developing an event. Also, we will additionally conduct a propensity score weighting analysis based on the covariates collected for this study. An additional sensitivity analysis may be done to adjust for the drop-in effect of patients receiving anti-cancer medications during follow-up.

A literature review of published data at the time of the final study report will be performed for the relevant endpoints. If there is any relevant scientific data publicly available by the time when the study ends (> 12 years later), Amgen will provide a comparative analysis. If a sufficient number of patients are identified in publicly available database with information on relevant confounding factors, Amgen will conduct a direct comparative analysis, but descriptive analyses will be undertaken either way.

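### Incidence endpoints are compared between arms by logistic regression with no time-at-risk term, so the test departs from its nominal 5% if observation time differs by arm

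*Protocol*

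**What the plan says.** The primary objective (Section 8.1) is worded as incidence: "To estimate incidence of neuropsychomotor developmental impairment, endocrine impairment, neurological impairment, and immune system impairment". Section 7.3 adds that the two treatments will be compared on these four domains. The Data Analysis part of the Abstract assigns the models: "A multivariate logistic regression will be used to compare incidence event objectives and Cox regression will be used to compare time-to-event objectives". Section 9.7.2.2.3 repeats the assignment: "The primary and secondary endpoint of discrete events (eg, incidence endpoints) will be compared by a logistic regression which will generate an odds ratio", and then "Endpoints that are time-to-event will be compared by a Cox regression model". The same section says "KM estimates for time to first onset of each specified event will be provided", but attaches no between-arm test to those curves. Section 9.7.2 mentions logistic or Cox models without saying which endpoint gets which.

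On observation time, Section 9.2.5 says that "data collection will end at 12-years of follow-up, the age of 25 years, loss-to-follow-up, withdrawal of consent, or death, whichever occurs earliest", and Section 9.2.1 sets the same limits. Section 9.7.2.2.3 adds that "events that occur after a relapse or secondary malignancy will be censored".

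For adjustment, Section 9.7.2.2.3 takes covariates from Section 9.3.2 that differ between arms at p < 0.25 and adds a propensity score weighting analysis. Observation time is not on the Section 9.3.2 list. The comparison is made only if each arm has at least 50 patients and the groups are comparable.

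**The concern.** The protocol censors events but compares the primary endpoints with a model that has no place for censoring. Logistic regression of ever versus never tests whether the proportions with an observed event are equal. That proportion depends on the event rate and on how long patients are watched. A patient who relapses at month 6 and a patient followed for 12 years without impairment enter the model as the same non-event.

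The groups are not randomised, and relapse and survival are themselves secondary outcomes that may differ. If one arm has better disease control, it is observed longer and looks more toxic at the same event rate. If it relapses more, real harm can be hidden. Either error would fall on the primary comparison of a post-authorisation safety study.

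**Working it through.** **1. The plan's own figures.** Section 9.5 divides 52 long-term survivors per arm by a 35% survival rate: 52/0.35 = 148.6, so 149 per arm and 298 in total. This reproduces. The two-sided pooled z-test of 98% versus 88% with 52 per arm gives p = 0.0457 (stated 0.0455). Below I use 149 per arm and take 35% as the proportion still observed at 12 years in one arm. Section 9.5 gives 35% as survival and applies it to both arms. The other arm's value is my assumption.

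**2. Follow-up is unequal between patients.** Section 7.2 describes patients treated before age 18. Because 25 − 12 = 13, anyone older than 13 at transplant cannot complete 12 years. Death, relapse, second malignancy, loss and withdrawal shorten follow-up further.

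**3. Same hazard, fixed unequal follow-up.** Let p12 be the 12-year incidence. With a constant hazard, the incidence by year t is p(t) = 1 − (1 − p12)^(t/12). The rejection probability is about Φ((|p1 − p2| − 1.96·SE0)/SE1), with SE0 pooled and SE1 unpooled. Example: p12 = 50% gives p(8) = 1 − 0.5^(8/12) = 37.0%. The odds ratio is (0.5/0.5)/(0.370/0.630) = 1.70. With 149 per arm, SE0 and SE1 are both about 0.057, so the probability is about Φ(0.31) = 62%.

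| p12 | 12 years vs 8 years | Odds ratio | Rejection, 149 per arm |
|---|---|---|---|
| 20% | 20.0% vs 13.8% | 1.56 | 30% |
| 50% | 50.0% vs 37.0% | 1.70 | 62% |
| 85% | 85.0% vs 71.8% | 2.23 | 80% |
| 98% | 98.0% vs 92.6% | 3.90 | 59% |

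At 12 versus 10 years the rejection probability is 10% to 24%. With 50 per arm at 12 versus 8 years it is 13% to 36%.

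**4. Random truncation, one case by hand.** With event hazard λ and truncation hazard μ, where exp(−12μ) = q is the proportion not truncated by 12 years, the observed proportion is λ/(λ+μ) × (1 − exp(−12(λ+μ))). For λ = 0.1 per year:
- q = 35%: μ = 0.0875, observed proportion 47.7%
- q = 50%: μ = 0.0578, observed proportion 53.8%

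The hazard is identical, yet the proportions differ by 6 points. Simulation gave 47.8% and 53.8%; logistic regression rejected in 19.6% of studies and a rate test in 4.8%. With early truncation (exponential, mean 1.5 years, in the truncated fraction) the proportions were 33.0% and 41.4%, and the rejection rates 31.7% and 5.2%.

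**5. Simulations with identical event hazards in both arms.** First set-up: hazards of 0.05 to 0.2 per year, early or constant truncation.

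| Per arm | Observed at 12 years | Logistic rejects | Rate test |
|---|---|---|---|
| 149 | 35% vs 35% | 4–6% | 4–6% |
| 149 | 35% vs 45% | 8–21% | 4–6% |
| 149 | 35% vs 50% | about 12–45% | 4–6% |
| 149 | 35% vs 55% | 18–67% | 4–6% |
| 50 | 35% vs 50% | 7–19% | 4–6% |

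Second set-up: 149 per arm, follow-up equal to the smallest of 12 years, 25 minus age, and an exponential time to death or relapse.

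| Free of death/relapse at 12 years | Mean years at risk | Logistic rejects at p12 = 20/50/85/98% | Cox score test |
|---|---|---|---|
| 35% vs 50% | 7.1 vs 8.3 | 7/12/21/24% | 4–6% |
| 35% vs 60% | 7.1 vs 9.0 | 10/25/46/52% | 4–6% |
| 20% vs 50% | 5.8 vs 8.3 | 17/45/74/79% | 4–6% |

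**6. Where the effect is small.** A moderate age imbalance (4–18 versus 0–14 years, equal truncation, 149 per arm) leaves logistic rejection near 5%. In the 35% versus 60% case, rejection is 4% if 98% have their event by year 1, 11% if 98% have it by year 2, and 29% if 85% have it by year 2.

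**The case against.** The strongest objection concerns the estimand. Death and relapse are competing events. With no other truncation, the proportion ever observed with an event by 12 years is the 12-year cumulative incidence with death and relapse as competing events, which is a legitimate quantity. In the example of 33.0% versus 41.4%, a direct comparison of these incidences has expected z = 0.084/√((0.330×0.670 + 0.414×0.586)/149) = 1.5 and rejects about 32% of the time, as logistic regression does. This stands. A cumulative-incidence contrast does not cure the problem; it answers a different question. But the protocol says these events are censored, and for age 25, loss and withdrawal a non-event reading has no such defence.

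Other points also stand in part:
- The protocol makes follow-up unequal between patients, not between arms, and plans with one 35% survival rate for both.
- Section 9.5 expects haematological toxicity during therapy and immune complications after treatment ends. For events that nearly all come early the inflation is small.
- Section 9.7.2.2.3 refers to all of Section 9.3.2, which includes a follow-up list, while Section 9.9 speaks of baseline characteristics. It would therefore be wrong to say that adjustment uses only baseline variables. Neither list contains observation time.
- Cox models and Kaplan-Meier estimates are in the plan, and the comparison depends on the groups being comparable. However, Cox is kept for endpoints classed as time-to-event, and the incidence endpoints are assigned to logistic regression.

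**Conclusion.** The point holds in conditional form. The protocol pairs a censoring rule with a model that cannot censor, and does so for its primary endpoints. If observation time differs by arm, the logistic test does not hold its 5% level for the hypothesis of equal event rates under observation. At 149 per arm and 35% versus 50% still observed, it rejects in about 12–45% of studies, or 7–24% with the age-25 cap, against 4–6% for a rate or Cox test.

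These figures assume constant event hazards, truncation independent of the event, no covariate adjustment, and arm-specific truncation values that the documents do not give. The top of the first range depends on the truncation pattern and event rate.

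A reader might infer that the arms will be followed unequally, or that the primary comparison will give a false signal. The documents support neither: with equal truncation logistic regression is valid, and the direction of any imbalance is unknown. The concern is mainly for domains where onset may come later, such as endocrine and neurodevelopmental impairment.

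**What to change.** In the Abstract (Data Analysis) and Sections 9.7.2 and 9.7.2.2.3, make the between-arm comparison of each primary incidence endpoint a cause-specific Cox regression of time to first onset. Censor at relapse, second malignancy, death, age 25, loss or withdrawal. Keep logistic regression only for outcomes assessed over a fixed window that all patients complete. Report observation time by arm beside each comparison.

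If cumulative incidence at fixed times is added, present it as a separate absolute-risk estimand with death and relapse as competing events. Differences in those events still affect it, so it does not replace the Cox comparison.

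The cost is wording. Onset dates are already needed for the Kaplan-Meier estimates and Cox models are already planned, so no new data are required. The headline becomes a hazard ratio instead of an odds ratio, and Cox regression does not remove informative censoring.

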9.5 Study Size

The targeted sample size for this study is approximately 298 patients. However, the actual number of patients that will be included in the study will depend on the results of site feasibility, willingness of patients (or their legal guardians/caregivers) or sites to participate in the study.

According to Marshall et al 2013, paediatric ALL patients are expected to have toxicity during intensification of therapy, generally related to hematological counts (Marshall et al, 2013). All patients also expect to have some immune complications after treatment end (Perkins et al, 2017) that will persist for some time.

Assuming that between 85%-98% of all patients will have at least one event, the expected ranges of sample sizes and relevant 95% CI is provided below. If 100 patients are enrolled.

95% C	onfidence	Interval o	of Estimated	Incidence o	of Adverse	Events by	Sample
-------	-----------	------------	--------------	-------------	------------	-----------	--------

S	ize	

Enrolled N Per Arm	Estimated Incidence of events	95% Confidence Interval*
150	98%	94.3%-99.3%
150	90%	84.1%-93.9%
150	85%	78.4%-89.8%
100	98%	93%-99.5%
100	90%	82.5%-94.5%
100	85%	76.7%-90.7%
75	98%	90.8%-99.3%
75	90%	82.0%-95.4%
75	85%	75.6%-91.6%
50	98%	89.5%-99.7%
50	90%	78.6%-95.7%
50	85%	71.5%-91.7%

* Wilson score interval

Sample size calculation for comparison analyses was calculated based on the number of long-term survivors needed. A risk difference of 10% (98% vs 88%) is considered as clinically significant. If the sample size is 52 long-term survivors per arm (104 in total), then a risk difference of as little as 10% will be detectable (p-value < 0.05).

Number of Long-term Survivors per Arm	Observed Risk Difference	P-value*
52/52	98% vs 88% = 10%	0.0455
40/40	98% vs 86% = 12%	0.0477
30/30	98% vs 83% = 15%	0.0477
20/20	98% vs 77% = 21%	0.0444

* z-test of two proportion comparison

Assuming a 35% long-term survival rate, the required number of patients entering the study per arm is 149 (52/0.35). Therefore, the number of patients entering the study needed to successfully fulfill the primary objectives while taking into account the 35% survival rate is 298.

Even though long-term survivors contribute the most essential data to this study, all enrolled patients contribute important information. If the total sample size is 149 patients per arm (298 in total), then a risk difference of as little as 5% will be detectable (p-value < 0.05).

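### Clinical relevance is set as a 10-point risk difference, but the adjusted comparison of incidence is an odds ratio, and at small enrolment the sizing composite has too few non-events to estimate it reliably

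*Protocol*

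**What the plan says.** Protocol section 9.5 fixes the scale on which the comparison is judged: "A risk difference of 10% (98% vs 88%) is considered as clinically significant". The comparison is sized on that difference with an unadjusted test, footnoted as a "z-test of two proportion comparison". The condition reads "If the sample size is 52 long-term survivors per arm (104 in total"), and the conclusion drawn from it is "then a risk difference of as little as 10% will be detectable (p-value < 0.05"). The survivor count is then inflated: "Assuming a 35% long-term survival rate, the required number of patients entering the study per arm is 149 (52/0.35"), hence 298 in total. The rates refer to a composite: "Assuming that between 85%-98% of all patients will have at least one event".

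The analysis sections use another scale. The Abstract (Data Analysis) says: "A multivariate logistic regression will be used to compare incidence event objectives". Section 9.7.2 names logistic or Cox models that give an odds ratio or hazard ratio. Section 9.7.2.2.3 says of discrete primary and secondary endpoints that they "will be compared by a logistic regression which will generate an odds ratio and 95% confidence interval of the odds of developing an event".

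Three further provisions matter:

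- The comparison runs only if at least 50 patients per arm are enrolled and the groups are comparable. No condition concerns the number of events or non-events.
- Covariates from the section 9.3.2 list that differ at p < 0.25 are considered for adjustment. Section 9.9 is firmer and puts differing baseline characteristics into the models.
- A propensity score weighting analysis is added. Its effect measure is not stated.

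Section 9.7.2.2.3 also provides incidence proportions with 95% CIs, and section 9.7.2 presents all analyses by treatment group.

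**The concern.** Two difficulties follow from setting relevance on one scale and reporting the adjusted result on another.

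First, this is a non-randomised comparison, and section 9.9 concedes that confounding is possible. The adjusted result is the one that should be held against the 10-point criterion, yet it arrives as an odds ratio. With event rates near 90% or above, an odds ratio is far from the risk ratio and can be misread as a large relative risk. That matters in a safety study done as a regulatory commitment.

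Second, when almost everyone has the event, the information in a logistic model comes from the few patients who do not. The 50-per-arm condition counts patients, so the comparison can be triggered with only a handful of non-events. The p < 0.25 screen can then add covariates without regard to that number.

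**Working it through.** **Inputs.** From section 9.5: 98% vs 88%, 52 survivors per arm, 35% long-term survival, 149 enrolled per arm, 85-98% with any event. From sections 9.7.2 and 9.7.2.2.3: minimum of 50 per arm, screen at p < 0.25. Assumed here: 20 to 25 usable covariates in section 9.3.2, and a rule of thumb of 5 to 10 non-events per model parameter.

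**Plan's own figure.** Pooled z-test, n = 52: z = 0.10 / √(2 × 0.93 × 0.07 / 52) = 1.998, two-sided p = 0.0457 (stated 0.0455). 52/0.35 = 148.6, so 149 per arm and 298 in total. Both reproduce.

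**Same contrast on three scales.**

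- Risk difference: 0.98 − 0.88 = 0.10
- Risk ratio: 0.98/0.88 = 1.11
- Odds ratio: (0.98/0.02)/(0.88/0.12) = 6.68

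**Non-events.** Expected number = n(1 − 0.98) + n(1 − 0.88). Chance of none in the 98% arm = 0.98^n.

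| n per arm | Expected non-events | Chance of none in 98% arm |
|---|---|---|
| 50 | 1.0 + 6.0 = 7.0 | 36% |
| 52 | 1.04 + 6.24 = 7.3 | 35% |
| 149 | 2.98 + 17.88 = 20.9 | 4.9% |

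With no non-event in one arm, the odds ratio runs to infinity, or to zero if the reference group is switched. Over the stated 85-98% range, taking both arms at the same rate, total non-events run from 15.6 (85%) to 2.1 (98%) at 52 per arm, and from 44.7 to 6.0 at 149 per arm.

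**The sizing test against the planned model.** On the expected counts at 52 per arm, without covariates, SE(log OR) = √(1/50.96 + 1/1.04 + 1/45.76 + 1/6.24) = 1.079. The odds ratio is 6.68 with Wald 95% CI 0.81 to 55.3 and p = 0.078. At 149 per arm the interval is 1.92 to 23.3.

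**Room for adjustment.** At 10 or 5 non-events per parameter, 7.3 non-events support 0.7 or 1.5 parameters, and 20.9 support 2.1 or 4.2. Treatment takes one of them. A screen at p < 0.25 passes a quarter of covariates by chance alone: 5 of 20, or about 6 of 25. That is 7.3/5 = 1.5 to 7.3/6 = 1.2 non-events per covariate at 52 per arm, and 20.9/5 = 4.2 to 20.9/6 = 3.5 at 149.

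**Simulation** (400 runs per setting, 98% vs 88%, independent covariates with no effect on outcome; medians are over estimable runs only).

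| Covariates | 52 per arm: not estimable | 52 per arm: median OR | 149 per arm: not estimable | 149 per arm: median OR |
|---|---|---|---|---|
| 0 | 37% | 4.3 | 5% | 7.0 |
| 5 | 44% | 5.2 | 4% | 7.1 |
| 10 | 56% | 7.8 | 7% | 7.1 |
| 15 | 67% | 14.0 | 7% | 8.0 |

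At 149 per arm the fit usually succeeds, and the estimate drifts visibly only with many covariates. At 52 per arm the odds ratio is unreliable even without covariates.

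**The case against.** Several points on the other side stand.

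- A reader might infer that the result cannot be compared with the 10-point criterion at all. The protocol does not support that. Proportions with CIs are reported by group, so the crude difference is available, and the weighting analysis leaves its measure open. What is missing is a named adjusted difference.
- A reader might infer that the model cannot be fitted. That is a fair description at 50-52 per arm, but not at the planned 149. Section 9.5 says all enrolled patients contribute, and nothing restricts the regression to survivors.
- A reader might extend the shortage to every primary endpoint. The 85-98% refers to any event. No rates are given for the neuropsychomotor, neurological, endocrine or immune domains.
- The covariate load is not fixed. Section 9.3.2 includes items that cannot be screened between groups, such as the number of blinatumomab cycles, and section 9.7.2.2.3 says only that differing covariates are evaluated.
- Sizing on a risk difference and testing by logistic regression is common, and both test the same null. At 52 per arm a likelihood-ratio test on the expected counts gives 2ΣO ln(O/E) ≈ 4.4, p about 0.04, so the Wald p of 0.078 partly reflects the choice of test.
- If first onset is analysed by Cox regression, 50.96 + 45.76 ≈ 97 of 104 patients have events, so sparseness does not arise there. A hazard ratio is still not a risk difference.
- The comparison is conditional, and the listed primary objective is to estimate incidence.

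These points narrow the finding. They do not supply an adjusted result on the scale of the criterion, and they do not change what happens if the comparison is run at or near the protocol's own minimum enrolment.

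**Conclusion.** The point holds in limited form, as a cheap improvement. The protocol judges relevance by a risk difference but fixes an odds ratio as its adjusted comparison for incidence endpoints. For the sizing composite at 98% vs 88%, that turns a risk ratio of 1.11 into an odds ratio of 6.68. At 50 enrolled or 52 survivors per arm, about 7 non-events are expected, and there is no finite odds ratio about one time in three. At 149 per arm, about 21 non-events allow a fit with a 5% chance of an empty cell, but not adjustment by everything that passes the p < 0.25 screen.

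The empty-cell figures rest on the protocol's rates. The limit on adjustment also rests on the assumed covariate count and the assumed rule of thumb. The documents do not support saying that the model fails at the planned size, or that the single domains have too few non-events.

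**What to change.** In section 9.7.2.2.3, and correspondingly in the Abstract and section 9.7.2:

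- State that the propensity-weighted analysis reports a risk difference with 95% CI, and that this is the main comparison for incidence endpoints. The propensity model is limited by the size of the treatment groups and not by the number of non-events, so it can carry more covariates than the outcome model.
- Keep the odds ratio as supportive, fitted with Firth's penalty so that it stays finite with an empty cell.
- Limit the number of covariates in the outcome model by the smaller of events and non-events, instead of by the p < 0.25 screen alone.

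The cost is wording plus some extra analysis work. No new data are needed, and the weighting is already planned. The downside is that a weighted risk difference is also imprecise when an arm has almost no non-events, and a simple Wald interval can then be too narrow. The interval method must suit sparse data. One option is to build it from Wilson-type limits, which section 9.5 already uses for single proportions.
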